## **6.7 COVID-19 Impact**

COVID-19 impact will be assessed by treatment group and overall only for the combined population sample of OL rimegepant treated or follow-up subjects. Analyses are based on COVID-19 visit impact data with non-missing COVID-19 visit dates (see Section 7.3).

Measurements will be slotted into safety analysis periods according to COVID-19 visit dates.

When COVID-19 visit impact is summarized descriptively over time, measurements will be first slotted into safety analysis periods. Next, measurements will be slotted into analysis visits in these analysis periods (see Section 7.5).

### **6.7.1 COVID-19 Overall Impact**

COVID-19 overall impact will be tabulated as the number and percentage of subjects in the categories defined by COVID-19 visit impact type, visit impact characteristics, and visit impact relationship (see Section 9.1.1). In addition, for each of the 3 COVID-19 visit impact type categories (i.e., missed visit; in-person visit at site; remote visit), the number and percentage of subjects in the following subcategories defined by the number of visits impacted by COVID-19 will be tabulated:  $\geq 2$  visits,  $\geq 3$  visits,  $\geq 4$  visits, etc. Visit counts are based on unique COVID-19 visit dates. Percentages are based on subjects with  $\geq 1$  visit with non-missing COVID-19 visit impact in the on-OL rimegepant or follow-up safety analysis period (see Section 9.1.3).

### **6.7.2 COVID-19 Impact Over Time**

COVID-19 visit impact will be tabulated over time at each analysis visit. The number and percentage of subjects in the categories defined by COVID-19 visit impact type, visit impact characteristics, and visit impact relationship will be presented at each analysis visit in the on-OL rimegepant and follow-up safety analysis periods. If a subject has multiple values (e.g., scheduled missed visit and unscheduled remote visit) in an analysis visit window, then all results will be presented. Percentages are based on subjects with  $\geq 1$  non-missing COVID-19 visit impact in the analysis visit window (see Section 9.1.3).

Missing LFT data impacted by COVID-19 will be tabulated over time at each analysis visit in the on-OL rimegepant and follow-up safety analysis periods as the number and percentage of subjects in the following categories:

1. Missing LFT data, defined as missing values for all of the 4 following LFTs in the analysis visit window: ALT, AST, ALP, and TBL.
2. Missing LFT data at visits impacted by COVID-19, i.e., meeting criteria (1) and having  $\geq 1$  visit impacted by COVID-19 in the analysis visit window (see Section 9.1.3)
3. Missing LFT data at missed visits due to COVID-19, i.e., meeting criteria (1), (2), and having  $\geq 1$  missed visit in the analysis visit window (see Section 9.1.1).

Percentages are based on evaluable subjects at each analysis visit. At an analysis visit in the on-OL rimegepant safety analysis period, evaluable subjects are OL rimegepant treated subjects with (OL rimegepant end date – study drug start date + 1)  $\geq$  lower bound of the analysis visit window. At an analysis visit in the follow-up safety analysis period, evaluable subjects are follow-up subjects with (last contact date – study drug last date + 1)  $\geq$  lower bound of the analysis visit window.

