⁸ The electronic subject diary (eDiary) will be dispensed at the Screening Visit, after all Screening Procedures are completed. The subject will be trained on the use of the eDiary. The subject will use the eDiary every day during the Observation Period and Treatment Phase to report migraine occurrence, migraine severity and if the subject treated the migraine.

⁹ Subjects who do not complete the Double-blind, Treatment Phase or do not enter the Open-label, Extension Phase should complete the End of Treatment Visit and 2-Week and 8-Week Follow-up Safety Visits.

¹⁰ While on-study, all visit windows are used for scheduling purposes and all efforts should be made to return subjects to the 28-day schedule if scheduling changes are made at any previous visit(s).

¹¹ The duration between the Pre-Randomization Lab Visit and the Randomization Visit is 4 days. The “+2” days window is included **for scheduling purposes only**. Every effort should be made to collect the Pre-Randomization Lab Visit samples as close to, and within, the 4 days prior to the Randomization Visit as possible. However, for scheduling convenience, this window may be up to 6 days (between the Pre-Randomization Lab Visit and the Randomization Visit).

Table 2. Schedule of Assessments – Open-label Extension Phase Including End of Treatment (EOT)¹⁰ & Follow-up Visits

Procedure	Phone visit to confirm eligibility based on laboratory criteria¹	Week 14 (Day 98 ± 3 days)	Week 16 (Day 112) and 20 (Day 140) (±3 days)	Visits every 4 weeks Week 24 (Day 168) to Week 64 (Day 448) / EOT (±3 days)	2-Week Follow-up Safety Visit (14 days after EOT visit ± 2 days)	8-Week Follow-up Safety Visit (8 weeks (-2 days to +14 days) after EOT visit)
Confirm Week 12 Laboratory Results	X					
Rescue Medication paper diary, Concomitant Medication paper diary and Menstrual Period paper log (female subjects) ²		X	X	X	X ³	X (Concomitant Medication paper diary only) ³
Safety Assessments						
Physical Examinations			X (Week 16 only)	X (Week 24 and 64 / EOT only)		
Vital Signs / Physical Measurements ⁴			X	X	X	
Clinical Safety Laboratory Testing			X (Week 16 only)	X (Week 24, 48, and 64 / EOT only)		
Liver function tests (LFTs)		X	X	X	X	X
Lipid Panel				X (Week 24 and 64 / EOT only)		
ECG			X (Week 16 only)	X (Week 24, 48, and 64 / EOT only)	X	
Urinalysis				X (Week 64 / EOT only)		
Pregnancy Test			X (urine)	X (urine)	X (urine)	X (serum)

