- **OL rimegepant treated subjects:** Enrolled subjects who received at least one dose of OL rimegepant, i.e., non-missing OL rimegepant start date.
  - **Interim subjects:** OL rimegepant treated subjects with OL rimegepant start date – DBT last date  $> 7$  days.
- **DB or OL rimegepant treated subjects:** Enrolled subjects who received at least one dose of rimegepant (DB or OL) i.e., non-missing DB or OL rimegepant start date. This corresponds to the Rimegepant Safety Analysis Set in the BHV3000-305 Protocol.
- **Follow-up subjects:** Treated subjects whose last contact date is in the follow-up safety analysis period.
- **Coronavirus Disease 2019 (COVID-19) impacted:** Enrolled subjects who are impacted by COVID-19 (see Section 9.1.2).

See Sections 7.3 and 7.4 for derived dates and analysis periods, respectively.

---

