    - Efficacy date: (1) Complete reference time point date from any question from the evening report headache log or follow-up headache log, or (2) non-missing OL rimegepant date on a non-scheduled day (see Sections [7.6.2.2](#) and [7.6.2.3](#)).
    - OP start date: Earliest reference time point date from the OP epoch.
    - OP end date: Latest reference time point date from the OP epoch.
  - Miscellaneous composite dates
-

- Last DBT visit date: Maximum of the following: (1) latest eDiary reference time point date < OL rimegepant start date; (2) latest complete visit date from Visit Date CRF records without “follow-up” in foldername and visit date < OL rimegepant start date. This will be used to assess eDiary compliance.
- Last OLE visit date: Maximum of the following: (1) latest eDiary reference time point date ≥ OL rimegepant start date; (2) latest complete visit date from Visit Date CRF records without “follow-up” in foldername and visit date ≥ OL rimegepant start date. This will be used to assess eDiary compliance.
- Last DB or OL rimegepant visit date: Maximum of last DBT visit date and last OLE visit date for subjects whose as-treated treatment group is rimegepant; last OLE visit date/time for subjects whose as-treated treatment group is placebo. This will be used to assess eDiary compliance.
- Last contact date: (1) Earliest complete death date from the AE CRF, if it exists; (2) otherwise, the maximum complete date of the following: AE start/stop; COVID-19 visit only for in-person or remote visits; ECG; eDiary reference time point; informed consent; IWRS randomization; laboratory collection; menstrual period start/stop; non-study medication start/stop; physical measurement; procedure; rating scale; questionnaire; study completion/discontinuation from Subject Status CRF (DBT, OLE, follow-up); vital sign; visit.
- COVID-19 visit date: (1) Complete record date, if it exists; otherwise, complete date the visit was planned to occur for a missed visit (see Section 9.1.1).
- Death date: Last contact date derived only for subjects who died (see Section 6.5.1.1).

No imputations are performed on these derived dates. Complete dates are those with valid, non-missing day, month, and year.

See Section 7.6.2.1 for the reference time point date/time and epoch derivations.

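### The follow-up missing-LFT table in SAP 6.7.2 can drop the subjects whose missed COVID-19 visits it is meant to count

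*SAP*

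**What the plan says.** SAP 6.7.2 gives, for each follow-up analysis visit, three nested counts: no LFT result in the window; that plus at least one COVID-19-impacted visit in the window; and "Missing LFT data at missed visits due to COVID-19". For the percentages, "evaluable subjects are follow-up subjects with (last contact date – study drug last date + 1" reaching the lower bound of the window. Table 4 sets Follow-up Week 2 at days 8 to 21 and Follow-up Week 8 at days 22 to 70. Later results go to an extension visit shown only in listings.

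SAP 7.3 takes last contact date as the latest of many dates, unless a death date exists. They include "laboratory collection" and "study completion/discontinuation from Subject Status CRF (DBT, OLE, follow-up"). COVID-19 records are restricted: "COVID-19 visit only for in-person or remote visits". A missed visit still receives a COVID-19 visit date, namely "complete date the visit was planned to occur for a missed visit", and SAP 6.7 slots it into a visit window by that date.

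SAP 3 defines follow-up subjects by the same variable: "Treated subjects whose last contact date is in the follow-up safety analysis period". Under SAP 7.4 that period starts after last dose + 7 days. For open-label visits, 6.7.2 bases evaluability on the open-label rimegepant end date, so on dosing and not on contact.

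Protocol Table 2 puts the 2-week visit 14 ± 2 days after EOT, and the later one as "8-Week Follow-up Safety Visit (8 weeks (-2 days to +14 days) after EOT visit").

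**The concern.** The third category exists to count subjects who have no LFT because COVID-19 made them miss the visit. Under these definitions, the missed visit places the subject in the Week 8 window through its planned date but does nothing to make that subject evaluable there. A subject last heard from at the 2-week visit can thus be recorded as missing the Week 8 visit and still be absent from the table that measures the LFTs lost.

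The protocol (1.3.1) names possible LFT change as the primary identified adverse event of interest, and LFTs are a stated purpose of the 8-week visit (4.1, 4.3.6). A table of how much of that follow-up was lost should not depend on the subject having been contacted later.

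**Working it through.** The documents give no figure for missing follow-up LFTs, so there is none to reproduce. The check is on definitions, day counts and one identity.

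**1. Where the visits fall.** Follow-up day = g + d + 1, with g = days from last dose to EOT and d = days from EOT to the visit. I assume g = 0 to 3; the documents do not fix it.
- 2-week visit, d = 12 to 16: days 13 to 17 (g = 0) up to days 16 to 20 (g = 3), all below 22.
- 8-week visit as planned, d = 56: days 57 to 60, inside 22 to 70.

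A subject whose last contact is the 2-week visit is therefore not evaluable at Week 8, although the missed visit is slotted there. With a longer gap this can fail: at g = 7 the 2-week visit falls on days 20 to 24.

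**2. Removal from both rows.** Last contact on or before last dose + 7 is follow-up day 8 or earlier. Such a subject is not a follow-up subject under SAP 3 and appears at neither visit.

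**3. Direction.** An LFT collected in the Week 8 window has a laboratory date on or after day 22, so its subject is always evaluable. Everyone removed therefore lacks an LFT. Let N be the subjects without the contact filter, m those with no LFT in the window, and k those of the m with no contact from day 22.

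Reported rate = (m − k)/(N − k); unfiltered rate = m/N; difference = k(N − m)/[N(N − k)].

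This is positive whenever k > 0 and m < N, and zero if k = 0.

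**4. Category 3.** Let c subjects have no LFT and a missed COVID-19 visit in the window, j of them among the k removed. The count falls from c to c − j. The percentage (c − j)/(N − k) is below c/N when j/k > c/N, that is, when missed COVID-19 visits are commoner among those removed than among all. If none of those removed had one (j = 0), the category 3 percentage would rise slightly.

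**5. Illustration.** With p = m/N and s = k/m, reported rate = p(1 − s)/(1 − ps); N cancels. All values of p and s are assumed.

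| Truly missing, p | s = 0 | s = 25% | s = 50% | s = 75% | s = 100% |
|---|---|---|---|---|---|
| 5% | 5.0% | 3.8% | 2.6% | 1.3% | 0.0% |
| 10% | 10.0% | 7.7% | 5.3% | 2.7% | 0.0% |
| 20% | 20.0% | 15.8% | 11.1% | 5.9% | 0.0% |

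For example, p = 10% and s = 50% gives 0.05/0.95 = 5.3%.

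**6. An effect in the other direction.** At the protocol's latest allowed time, d = 56 + 14 = 70, the follow-up day is 71 (g = 0) to 74 (g = 3). Footnote 10 of Protocol Table 2 counts its timeframe from last dose, which also gives 70 + 1 = 71. An LFT done then falls outside days 22 to 70. Unless there is another LFT in the window, the subject is evaluable and counted as missing at Week 8.

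**The case against.** Missing the LFT removes nobody by itself. Last contact date draws on adverse event and non-study medication start and stop dates, procedures, any visit, remote COVID-19 contacts and the Subject Status date. Any one of these on or after day 22 keeps the subject in, counted as missing. The protocol's rationale for widening the 8-week window expects contact at that time with laboratory tests afterwards, and a remote contact counts. A reader might infer that everyone who missed the 8-week LFT drops out; the definitions do not support that. This part of the objection stands, and the number affected is unknown. The SAP does not say what date sites enter as the follow-up status date.

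Missed visits are also visible elsewhere. The first table in 6.7.2 covers open-label treated or follow-up subjects and has no last-contact filter, the 6.7.3 listing shows impact codes by visit, and 6.2.3.5 tabulates non-completion of follow-up. That limits the harm, but neither of the 6.7 outputs reports whether the LFT was obtained. It also means that two tables in one section can disagree about the same subject.

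A reader might further infer that the table as a whole understates missingness, or that it supports a claim of near-complete liver follow-up. Neither is established. The day-70 limit works the other way, so the net direction is uncertain, and no document makes such a claim.

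Finally, a denominator of subjects still under observation is an ordinary choice. That is fair in general, but it fits poorly here because the event being counted can itself end observation.

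**Conclusion.** The point holds in limited form. The contact rule in 6.7.2 can remove subjects with a recorded missed COVID-19 visit from the row meant to count them. Taken alone, it can only lower the overall missing percentage relative to the unfiltered population. Category 3 is the most exposed: its count can only fall, and its percentage falls under the condition shown above.

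The size depends on how many subjects had no dated contact from follow-up day 22. The documents do not give this, and it is zero if every such subject has a status date or other record by then. The day counts assume EOT within 3 days of last dose. The table is descriptive, feeds no hypothesis test, and is not the denominator for the LFT-elevation summaries in 6.5.2.2. This is a small correction worth making.

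**What to change.** For this table only, define evaluable at a follow-up visit as open-label rimegepant treated or follow-up subjects who meet either condition:
- last contact date − study drug last date + 1 is at or above the lower bound of the window; or
- a missed COVID-19 visit has its COVID-19 visit date (the planned date) in that window.

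Leave the three categories as they are. This restores every recorded missed COVID-19 visit to category 3. Subjects lost without such a record stay out, so a supplementary percentage based on all subjects expected at the visit is a useful option.

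A denominator based on time to database lock would be a poor substitute. At final lock it would bring in ordinary attrition and subjects who finished before 01MAR2020, when the COVID-19 form starts (SAP 9.1.1), and would blur a COVID-19 table.

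Separately, the upper bound of day 70 in Table 4 and the protocol's +14-day allowance must be reconciled, so that the status of an LFT done on day 71 or later is explicit.

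The cost is a sentence of SAP text, a changed denominator and a rerun of one table. Reported missingness becomes slightly less favourable. Version 10.0 was already revised after final lock, so the change should be labelled as made after lock.

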### 6.7.3 COVID-19 Impact Listings

A by-subject listing of COVID-19 impact codes by visit will display visits with abbreviated labels (e.g., W36 = OL rimegepant Week 36; FU2 = Follow-up Week 2) in separate columns. Spanning headers above the visits display the safety analysis period (OL rimegepant or follow-up). Each column denotes an analysis visit and displays the COVID-19 visit impact code (see Section 9.1.5.1). If a subject has multiple COVID-19 visit impact codes in an analysis visit window, then results are displayed sorted by COVID-19 visit date and comma-concatenated across all COVID-19 visit dates in the analysis visit window (e.g., “#U,&M1” if “#U” has a visit date of 01MAY2020 and “&M1” has a visit date of 10MAY2020). Footnotes will describe the abbreviations in the COVID-19 visit impact code (see Section 9.1.5.2).

A by-subject listing of COVID-19 visit impact will display analysis period, analysis visit, COVID-19 visit date, study day derived from COVID-19 visit date, rimegepant study day derived from COVID-19 visit date, visit impact status, visit type, visit impact type, visit impact characteristics, visit impact relationship with specify text, and premature study termination (see Section 9.1.1).

## 7 CONVENTIONS

### 7.1 General

#### 7.1.1 Output Layout

Refer to the BHV3000 Core SAP for TLF layout conventions.

---

For the CSR and Addendum Report, a list of TLFs and unique TLF templates will be provided in the corresponding Mock TLF documents.

For the 90-Day Safety Update, a list of TLFs will be provided in the 90-Day Safety Update List of Deliverables, which will cross-reference (but not display) TLF templates in the Mock TLF CSR document. Output will be by overall, not treatment group.

### **7.1.2 Duplicate Subjects**

Duplicate subjects are those who enrolled in a previous BHV3000 study or rescreened more than once in study BHV3000-305 (either as per protocol or due to non-compliance), and are assigned more than 1 subject identifier in the BHV3000 project. These subjects will be identified from the (1) Demographics CRF which captures the previous BHV3000 subject identifier, and (2) Rescreen CRF which captures the previous BHV3000-305 subject identifier. The following conventions will apply:

- The unique subject identifier will be derived from the protocol number, site number, and subject number corresponding to the first randomization or treatment across all BHV3000 studies in which the subject enrolled. Otherwise, the unique subject identifier will be derived from the subject identifier.
- The raw datasets will contain data from all BHV3000-305 subject identifiers, with the unique subject identifier populated across records.
- The analysis datasets will contain data as follows:
  - If the subject was randomized or treated more than once in study BHV3000-305, then data from all subject identifiers corresponding to randomization or treatment in study BHV3000-305 will be included.
  - If the subject was randomized or treated only once in study BHV3000-305, then only data from the subject identifier corresponding to randomization or treatment in study BHV3000-305 will be included.
  - If the subject was not randomized or treated in study BHV3000-305, then only data from the subject identifier corresponding to the last enrollment in study BHV3000-305 will be included.
  - The unique subject identifier and previous BHV3000-305 subject identifier will be populated across records.
- By-subject listings will display subject identifier, but not unique subject identifier.

### **7.2 Subgroups**

Not applicable.

### **7.3 Derived Dates**

Derived dates for defining analysis periods are defined as follows:

---

- eDiary reference time/point date/time: See Section 7.6.2.1.
  - eDiary dosing dates:
    - Study drug to treat headache or during aura date/time: Complete reference time point date/time from any of the following date/time questions: study medication to treat headache or during aura from the evening report headache log or follow-up headache log; additional study medication to treat headache or during aura from the evening report headache log.
    - Imputed OL rimegepant to treat headache date/time: Complete reference time point date/time from “yes” response to question about having already taken study medication to treat headache from the scheduled dosing report. Derived only if both of the following criteria are met:
      - Reference time point date/time on or after the IWRS Week 12 kit assigned local date/time
      - There are no complete reference time point dates on the same day as the “yes” response from any of the following questions: study medication to treat headache or during aura date/time from the evening report headache log or follow-up headache log; additional study medication to treat headache or during aura date/time from the evening report headache log; date of missed scheduled dosing report or evening report headache log from the medication reconciliation form; study medication date/time from the scheduled dosing report.
    - Study drug date/time: Study drug to treat headache or during aura date/time, imputed OL rimegepant to treat headache date/time, or complete reference time point date/time from any of the following questions: date of missed scheduled dosing report or evening report headache log from the medication reconciliation form (note that time is not collected); study medication date/time from the scheduled dosing report.
      - DBT: Reference time point date/time before the IWRS Week 12 kit assigned local date/time (reference time point date before the IWRS Week 12 kit assigned local date for medication reconciliation form data) or the IWRS Week 12 kit assigned local date/time missing
      - OL rimegepant: Reference time point date/time on or after the IWRS Week 12 kit assigned local date/time (reference time point date on or after the IWRS Week 12 kit assigned local date for medication reconciliation form data)
    - Study drug start date/time: Earliest study drug date/time.
    - Study drug end date/time: Latest study drug date/time.
    - Study drug last date/time:
      - Interim database lock: Study drug end date/time date derived only for subjects who have either (1) non-missing DB completion status on the DB Subject Status CRF, not continuing to OL on the DB Subject Status CRF, and missing OL rimegepant start date/time, or (2) non-missing OL completion status on the OL Subject Status CRF.
      - Final database lock: Study drug end date/time.
-

- DBT start date/time: Earliest DBT study drug date/time. This should be equal to study drug start date/time.
  - DBT end date/time: Latest DBT study drug date/time.
  - DBT last date/time:
    - Interim database lock or snapshot prior to Week 12 Interim Analysis database lock: DBT end date/time date derived only for subjects with non-missing DB study completion status on DB Subject Status CRF.
    - Database locks at or after Week 12 Interim Analysis database lock: DBT end date/time.
  - OL rimegepant start date/time: Earliest OL rimegepant study drug date/time.
  - OL rimegepant end date/time: Latest OL rimegepant study drug date/time.
  - OL rimegepant last date/time:
    - Database lock or snapshot prior to final database lock: OL rimegepant end date/time date derived only for subjects with non-missing OL study completion status on OL Subject Status CRF or non-missing follow-up study completion status on the Follow-up Subject Status CRF.
    - Final database lock: OL rimegepant end date/time.
  - DB or OL rimegepant start date/time: Study drug start date/time for subjects whose as-treated treatment group is rimegepant; OL rimegepant start date/time for subjects whose as-treated treatment group is placebo.
  - DB or OL rimegepant end date/time: Study drug end date/time for subjects whose as-treated treatment group is rimegepant; OL rimegepant end date/time for subjects whose as-treated treatment group is placebo.
  - DB or OL rimegepant last dose date/time: Study drug last date/time for subjects whose as-treated treatment group is rimegepant; OL rimegepant last date/time for subjects whose as-treated treatment group is placebo.
  - Other eDiary dates:
    - Headache start date/time: Complete reference time point date/time from the headache start question from the evening report headache log.
    - Headache end date/time: Complete reference time point date/time from the headache end question from the evening report headache log or follow-up headache log.
    - Efficacy date: (1) Complete reference time point date from any question from the evening report headache log or follow-up headache log, or (2) non-missing OL rimegepant date on a non-scheduled day (see Sections [7.6.2.2](#) and [7.6.2.3](#)).
    - OP start date: Earliest reference time point date from the OP epoch.
    - OP end date: Latest reference time point date from the OP epoch.
  - Miscellaneous composite dates
-

- Last DBT visit date: Maximum of the following: (1) latest eDiary reference time point date < OL rimegepant start date; (2) latest complete visit date from Visit Date CRF records without “follow-up” in foldername and visit date < OL rimegepant start date. This will be used to assess eDiary compliance.
- Last OLE visit date: Maximum of the following: (1) latest eDiary reference time point date ≥ OL rimegepant start date; (2) latest complete visit date from Visit Date CRF records without “follow-up” in foldername and visit date ≥ OL rimegepant start date. This will be used to assess eDiary compliance.
- Last DB or OL rimegepant visit date: Maximum of last DBT visit date and last OLE visit date for subjects whose as-treated treatment group is rimegepant; last OLE visit date/time for subjects whose as-treated treatment group is placebo. This will be used to assess eDiary compliance.
- Last contact date: (1) Earliest complete death date from the AE CRF, if it exists; (2) otherwise, the maximum complete date of the following: AE start/stop; COVID-19 visit only for in-person or remote visits; ECG; eDiary reference time point; informed consent; IWRS randomization; laboratory collection; menstrual period start/stop; non-study medication start/stop; physical measurement; procedure; rating scale; questionnaire; study completion/discontinuation from Subject Status CRF (DBT, OLE, follow-up); vital sign; visit.
- COVID-19 visit date: (1) Complete record date, if it exists; otherwise, complete date the visit was planned to occur for a missed visit (see Section 9.1.1).
- Death date: Last contact date derived only for subjects who died (see Section 6.5.1.1).

No imputations are performed on these derived dates. Complete dates are those with valid, non-missing day, month, and year.

See Section 7.6.2.1 for the reference time point date/time and epoch derivations.

